1. PROTOCOL SUMMARY

Title: Topical Ruxolitinib (Jak1/Jak2 inhibitor) in Chronic Hand Dermatitis attenuates inflammation and enhances skin barrier repair.

Principal Investigator: [name] [name];
[contact]

Single site: Department of Dermatology - University of Rochester Medical Center, Rochester, NY

Study phase: Open label, proof of concept study

Population: Females and Male, age 18 - 75 years, who have moderate to severe Chronic Hand Dermatitis (CHD)

Number of participants: Up to 25 will be enrolled with 15 completing full study term

Intervention: Ruxolitinib cream 1.5% is an investigational drug that will be applied twice daily (BID) for 12 weeks (IND exempt) by the study participant. Ruxolitinib (Other Name: INCB018424) cream is a topical formulation applied as a thin film to affected areas.

Objectives and Endpoints:Primary objective & outcome:

1. To assess the efficacy of Ruxolitinib cream 1.5% on skin lesions in patients with Chronic Hand Dermatitis:

- proportion of patients achieving an Investigators Global Assessment (IGA) score of 0 or 1 with at least a 2-step improvement (IGA treatment success) at week 12
- Hand Eczema Severity Index (HECSI)-75% from baseline to week 12

Secondary objective & outcome:

- To assess the efficacy of Ruxolitinib cream 1.5% on other clinical domains:
Time to IGA treatment success
- Change in HECSI score from baseline to week 4, 8 and 12.
- Proportion of subjects with a ≥ 2 and ≥ 4 -point improvement in Itch Numerical Rating Scale (NRS) score from baseline to week 12.
- HECSI-75% at week 8
- HECSI-90% at week 12

2. To assess safety and tolerability of Ruxolitinib cream 1.5% in patients with chronic hand dermatitis:

- incidence, frequency and severity of adverse events and laboratory data for hematology, serum chemistry and urinalysis
- use of rescue medications

Exploratory objective & outcome:

1. To assess the effect of Ruxolitinib cream 1.5% on patient reported outcomes
 - Change from baseline to week 4, 8 and 12 in DLQI
 - Change from baseline to week 4, 8 and 12 in work productivity and activity impairment index
2. To assess the efficacy of Ruxolitinib cream 1.5% on skin barrier integrity in patients with Chronic Hand Dermatitis:
 - change in transepidermal water loss (TEWL) and barrier integrity score (TEWL recovery after tape stripping) and pH from baseline to week 4 and end of treatment on perilesion (normal appearing) skin
3. To identify translational skin biomarkers

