3. STUDY POPULATION

Number of patients: Up to 25 total subjects. We might need to enroll additional subjects in case of subject early discontinuation to reach the total number of 15 evaluable subjects (complete data set).

Study population: Females and Male, age 18-75 years, who have Chronic Hand Dermatitis

Racial and Ethnic Origin: We will not have any restrictions based on racial or ethnic origin. We based our target research population racial and ethnic distribution on the data of the 2000 United States Census for the Monroe County Area.

Vulnerable subjects: We will not be targeting vulnerable subjects

Inclusion Criteria:

- Age 18-75 years.
- Diagnosis of chronic hand eczema defined as hand eczema, which has persisted for more than 3 months or returned twice or more within the last 12 months.
- Disease severity graded as moderate to severe according to IGA (i.e., IGA ≥ 2).
- Recent history (within 1 year before the screening visit) of inadequate response to topical corticosteroid and/or calcineurin inhibitors treatment or topical corticosteroid treatment being medically inadvisable.

Exclusion Criteria:

- Active atopic dermatitis in regions other than the hands requiring medical treatment.
- Active psoriasis in regions other than the hands requiring medical treatment.
- Clinically significant infection (e.g., impetiginized hand eczema or tinea manuum) on the hands.
- Patients with excessive contact of hands with water (longer than 2 hours a day; or > 20 hands washing at day) that is believed to be a predominant cause of the hand dermatitis.
- Subjects with known antigen sensitization based on Patch test (with 3 years) that are unable to reduce contact with the specific antigen(s).
- Subjects chronically and consistently exposed to known irritant or other substance known to impact skin barrier will be excluded based on PI judgement.
- Systemic treatment with immunosuppressive drugs, immunomodulating drugs, retinoids, or corticosteroids within 4 weeks prior to baseline.
- Systemic treatment with antibiotics within 4 weeks prior to baseline
- Phototherapy on the hands within 4 weeks prior to baseline.
- Use of topical immunomodulators (e.g., phosphodiesterase-4 (PDE-4) inhibitors, pimecrolimus, tacrolimus) or topical corticosteroids on the hands within 2 weeks prior to baseline.
- Use of topical antibiotics on the hands within 2 weeks prior to baseline.

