- **Disease status assessment:** **1)** Investigator Global Assessment (IGA), which will provide information of the overall disease (5-point scale: clear, almost clear, mild, moderate, severe) and it is the score requested by FDA for clinical study. Data will be reported as and **2)** Hand Eczema Severity Index (HECSI)^{viii}, a well-accepted and validated scoring system for disease activity. It incorporates both the extent and the intensity of the disease. Each hand is divided into five areas: fingertips, fingers (except the tips), palms, back of hands and wrists. Each area will be score for

extension and intensity of the six following clinical signs: erythema, induration/papulation, vesicles, fissuring, scaling and edema; which are graded on the following scale: 0, no skin changes; 1, mild disease; 2, moderate and 3, severe (see appendix). Data will be reported as percent change in HECSI score from baseline to week 4, 8 and 12.

The presence or absence of skin irritation (e.g. macular/papular eruption), redness, atrophy and telangiectasia will be noted at each study visit.

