- **Study Drug Diary:** subjects will be provided with a prepopulated dated calendar to record their twice daily (AM and PM) application of study medication as well as the time the medication is applied. Also, on this diary the subject can indicate if a missed dose occurred and there is a blank space they can write in the reason it was missed. At the END of each day the subject will need to indicate on the same study diary their level of hand dermatitis itch throughout the day – 0=no itch and 10=worst imaginable itch. Subjects will indicate their level 0-10 by circling the number that best applies to them for that particular date. Detailed instructions are provided on the Incyte Study Diary as well as contact information of coordinator.

Prohibited Medications and procedures: use of topical or systemic immunosuppression/immunomodulators medications and Phototherapy is not permitted during the study. Hand surgery or other procedures (including but not limited to Cryotherapy, ED&C, skin biopsy) are disallowed during the study. If medically necessary, the investigator will withdraw the patients from the study.

5. RISK, BENEFITS and PROTECTION AGAINST RISKS

Risks Associated with Digital Picture

There are no known risks for the digital picture. The image will not include identifying features and will be labeled with study subject ID and date. ~~Pictures will be taken with a dedicated camera, stored on a secure server.~~ Pictures will be taken through the Haiku App and stored in the patients EMR in Epic.

Risks Associated with Barrier Assessments

There are no known risks for the barrier assessments.

Risks Associated with Tape Stripping

The risks associated with tape stripping, theoretically, include the rare possibility of an allergic reaction to the tape and infection. Since the tape is removed immediately after application, the risk of reaction is extremely low. In previous and ongoing studies involving tape stripping, it has been noted that a very mild erythema may develop immediately after a series of tape stripplings on one localized area of skin, presumably due to the mild mechanical disturbance. The erythema is expected to resolve within 12 hours without sequelae. The risk of skin infection is extremely low since only superficial skin layers are removed. Subjects will be provided with wound care information and a department phone number to contact should they have any concerns.

Risks of Phlebotomy

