6. DATA ANALYSIS AND DATA MONITORING

Objectives and Endpoints:

Primary objective & outcome:

1. To assess the efficacy of Ruxolitinib cream 1.5% on skin lesions in patients with Chronic Hand Dermatitis:

- proportion of patients achieving an Investigators Global Assessment (IGA) score of 0 or 1 with at least a 2-step improvement (IGA treatment success) at week 12
- HECSI-75% from baseline to week 12

Secondary objective & outcome:

1. To assess the efficacy of Ruxolitinib cream 1.5% on other clinical domains (e.g. pruritus, pain, work productivity and activity impairment; daily quality of life index/DLQI, Hand Eczema Severity Index/HESI):

- Time to IGA treatment success
- Change in HECSI score from baseline to week 4, 8 and 12.
- Proportion of subjects with a ≥ 2 and ≥ 4 -point improvement in Itch Numerical Rating Scale (NRS) score from baseline to week 4, 8 and 12.
- HECSI-75% at week 8
- HECSI-90% at week 12

2. To assess safety and tolerability of Ruxolitinib cream 1.5% in patients with chronic hand dermatitis:

- Incidence, frequency and severity of adverse events and laboratory data for hematology, serum chemistry and urinalysis
- use of rescue medications

Exploratory objective & outcome:

1. To assess the effect of Ruxolitinib cream 1.5% on patient reported outcomes

- Change from baseline to week 4, 8 and 12 in DLQI

- Change from baseline to week 4, 8 and 12 in work productivity and activity impairment index
2. To assess the efficacy of Ruxolitinib cream 1.5% on skin barrier integrity in patients with Chronic Hand Dermatitis:
- change in transepidermal water loss (TEWL) and barrier integrity score (TEWL recovery after tape stripping) and pH from baseline to week 4 and end of treatment on perilesion (normal appearing) skin
3. To identify translational skin biomarkers
- change in the expression of selected biomarkers in skin samples obtained from tape stripping (d-squame) at baseline and end of treatment (week 12)
4. To identify change in microbiome after treatment

Side effects and baseline characteristics will be tabulated qualitatively. The blinded pre- vs post evaluation will be analyzed for IGA scores by the Wilcoxon sign-rank test.

Data Storage and Confidentiality

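### The one planned test measures shift in IGA, not week-12 response, and neither primary outcome has a stated interval, analysis set or missing-data rule

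*Combined protocol and SAP*

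**What the plan says.** Section 6 (Data Analysis and Data Monitoring) lists two primary outcomes. The first is the proportion of patients with an IGA "score of 0 or 1 with at least a 2-step improvement (IGA treatment success) at week 12". The second is "HECSI-75% from baseline to week 12", which the plan does not define further; by convention it means a reduction of at least 75% from baseline.

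The analysis text that follows is two sentences. One says that side effects and baseline characteristics will be tabulated. The other is "The blinded pre- vs post evaluation will be analyzed for IGA scores by the Wilcoxon sign-rank test". The post-treatment visit is not named, although section 4 has clinical scores taken at weeks 4, 8, 12 and 16.

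For HECSI, section 4 adds: "Data will be reported as percent change in HECSI score from baseline to week 4, 8 and 12". That is a percent change, not a responder proportion. The matching sentence for IGA breaks off in the text available, so nothing is claimed about it here.

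On numbers, section 1 plans "Up to 25 will be enrolled with 15 completing full study term". Section 3 says the study might "enroll additional subjects in case of subject early discontinuation to reach the total number of 15 evaluable subjects (complete data set"). Under prohibited medications and procedures, section 4 says: "If medically necessary, the investigator will withdraw the patients from the study".

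**The concern.** A single-arm study with a responder primary outcome has one main efficacy result: the response rate and its precision. Section 6 plans neither the interval nor the denominator, and it puts its one p-value on a different quantity.

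The signed-rank test responds to any change in IGA. On the 5-point scale (taken as scored 0 to 4), section 3 admits subjects with IGA of 2 or more. A subject who goes from 2 to 1 therefore counts as improved in the test and as a failure for the primary outcome. The test could come out small while few or no subjects meet the outcome, and it says nothing about HECSI-75.

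The denominator matters more. Replacing subjects who stop early until 15 have complete data suggests that response will be taken among completers. Subjects who need prohibited treatment are withdrawn, so some who are doing badly can leave that set and be replaced. A response rate taken that way can be too high, and the choice would otherwise be made after the data are seen.

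**Working it through.** **Inputs from the plan.** 15 evaluable subjects (sections 1 and 3); up to 25 enrolled (sections 1 and 3); IGA success needs a score of 0 or 1 and at least two steps (section 6). The plan states no alpha, power, expected response rate or dropout rate, so there is no sample size figure to reproduce. The pair 25 and 15 allows a loss of up to (25 − 15)/25 = 40%, which is arithmetic and not a stated rate.

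**Assumptions.** Two-sided 0.05; 15 evaluable subjects; the outcome counts below are illustrations.

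**Step 1: the test against the IGA outcome.** Zero changes are dropped. When all k non-zero changes are one step, every rank is tied at (k + 1)/2 and the exact test reduces to the sign test. With nobody worse, p = 2 × (1/2)^k.

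Six improve one step and nine are unchanged:
- Exact p = 2 × (1/2)^6 = 0.031.
- Normal approximation: ranks are 3.5, the rank sum is 21, its mean is 10.5 and its variance is 6 × 3.5²/4 = 18.375. So z = 10.5/4.287 = 2.45 and p = 0.014, or 0.020 with a 0.5 continuity correction.
- IGA successes: 0/15, exact 95% CI 0 to 21.8%. The upper limit is 1 − 0.025^(1/15).

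The result is sensitive to worsening:

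| Improved / worse (one step each) | Exact p | Approximate p | With continuity correction |
|---|---|---|---|
| 6 / 0 | 0.031 | 0.014 | 0.020 |
| 6 / 1 | 0.125 | 0.059 | 0.073 |
| 8 / 1 | 0.039 | 0.020 | 0.023 |

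In every row the number of IGA successes is zero. This shows that the two quantities can diverge, not how likely that is.

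**Step 2: the denominator.** Take nine successes, all among 15 completers, and count non-completers as non-success. The Clopper-Pearson limits for x of n are the 2.5% point of Beta(x, n − x + 1) and the 97.5% point of Beta(x + 1, n − x).

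| Non-completers | n/N | Response | Exact 95% CI |
|---|---|---|---|
| 0 (completers only) | 9/15 | 60% | 32.3 to 83.7% |
| 3 | 9/18 | 50% | 26.0 to 74.0% |
| 5 | 9/20 | 45% | 23.1 to 68.5% |
| 10 (bounding case) | 9/25 | 36% | 18.0 to 57.5% |

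Three non-completers move the estimate by 10 points, five by 15 and ten by 24. At the opposite extreme, counting all ten missing values as success gives (9 + 10)/25 = 76%.

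**Step 3: search for a rule elsewhere.** No other section gives an interval, an analysis set tied to an outcome, or a rule for missing week-12 data. Section 3 sets a target for enrolment and assigns it to no analysis.

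**The case against.** The strongest reply is that the plan never says the signed-rank test analyses the primary outcomes. The sentence speaks of a blinded evaluation, yet the study is open label and describes no blinded assessment, so it may refer to something separate. On that reading the test is not a wrong choice; the primary analysis is simply unwritten. A small proof-of-concept study with no null rate can also report its response proportions descriptively, and an IGA shift does bear on the general aim of efficacy on skin lesions.

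Much of this is fair, and no hypothesis test of the proportions is needed. But on either reading the two primary outcomes have no stated precision, denominator or missing-data rule, and small size makes a stated interval more useful.

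The six-improver example is constructed. It needs nobody to worsen and nobody to gain two steps, and no decision in the plan hangs on 0.05. It carries limited weight.

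The bias is possible, not shown. The withdrawal sentence follows a list of hand procedures as well as prohibited drugs, and such withdrawals need not be treatment failures. Consent is taken at screening and enrolment is not defined, so the 25 may include subjects who never applied drug. The 36% figure is therefore only a bound.

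Lastly, use of rescue medication is an outcome in section 6, and a missing-data rule alone does not say how a subject with rescue use and an observed week-12 score counts. That stands.

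**Conclusion.** The point holds and should be fixed. The only inferential analysis measures shift in IGA and addresses neither week-12 response outcome. Neither outcome has a stated interval, analysis set or missing-data rule. The completer target with replacement makes this more than missing detail, because the plan followed as written points to a response rate that can be biased upward. With nine successes and five non-completers counted as non-success, the difference is 60% against 45%. The size depends on the assumed number of successes and non-completers and on how the latter would have done. The finding that the denominator and precision are unspecified depends on none of these assumptions.

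**What to change.** Add to section 6 wording such as:

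> Primary analysis: IGA treatment success and HECSI-75 (at least 75% reduction from baseline) at week 12 will each be reported as n/N, percent and exact (Clopper-Pearson) two-sided 95% CI. N is all subjects who applied study drug at least once; a missing week-12 value counts as non-success. The same figures will be shown for the complete-data subjects.

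Keep the signed-rank test as a supportive description of IGA shift, with week 12 named as its post value. Section 6 should also say how a subject with rescue use and an observed week-12 score is counted in the analysis; the wording above leaves that open.

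The cost is a few sentences, with no new data, visits or patients. The intervals will be wide at this size. Counting missing values as non-success gives a lower, less favourable estimate. It is the low end of the range, which is why the complete-data figures sit beside it.

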7. SUBJECTS IDENTIFICATION, RECRUITMENT AND CONSENT

Method of subject identification and recruitment

[name] [name] and study team will identify potential subjects in URMC dermatology clinics, screening upcoming clinic schedules in eRecord for potential eligible subjects with a diagnosis of hand dermatitis as well as referrals from dermatologists within URMC dermatology clinics. The study team may contact the potential eligible subjects via telephone call prior to their clinic visit to discuss the study, field questions and assess interest. If a patient is found to have a history of diagnosed hand dermatitis in which they have been treated at URMC dermatology, as well as a history of having been seen by [name] [name] during a prior clinic visit, the potential subject may be contacted via URMC MyChart. If the potential subject is interested in participating in the study they will be offered to have the consent form mailed or emailed to them to READ ONLY with instructions that the consent is for review only. Prior to the consent being mailed or emailed to the potential subject a study team member will cross out the signature page to eliminate confusion. The potential participant will sign a NEW clean consent upon their clinic and/or study visit along with the study team member.

In the case of clinical subjects, [name] or other URMC faculties will provide the subject with a contact phone number for the study coordinator who is approved to enroll and consent subjects. While [name] will be available for questions, consent might be obtained by other study personnel for subjects she sees in her clinical practice. It will be made clear to the potential subjects that their participation is voluntary and their care at the Department of Dermatology will not be affected by their decision to participate in this study.

Process of consent

[name] or other team members (e.g. coordinator, nurse, co-investigator) will meet directly with the subjects in a private suite. The consent form will be discussed with the potential subject. Time allotted to consenting will be dependent on the subjects' needs, questions, and comprehension of the information in the consent form. Each subject will be encouraged to read the consent form on his/her own and ask any specific questions as well as have the option to take the consent home to review with family and/or friends.

Subjects will be given a copy of the signed consent.

Subject capacity

We will not be recruiting subject incapable of giving informed consent.

Subject/representative comprehension

The subject's capacity to comprehend the information in the consent form will be assessed by asking questions about the content and encouraging the subject to describe briefly the study procedures.

Documentation of consent

The consent will be documented by signing and dating the consent form by both the study subject and the person obtaining consent. A copy of the consent form will be provided to the subject.

Costs to the subject

Procedures performed during the study will be at no cost to the subject.

Payment for participation

Subjects that agree to participate in the study will receive compensation for their time: \$35.00 for the screening visit. Each complete study visit will be \$50.00. For a total of up to \$285.00 including if all visits are completed.

For this study we use a subject payment system called Advarra Participant Payments. The system allows three ways to provide payment. Subjects can choose: a reloadable debit card; direct deposit; or mailed paper checks. The study team will help subject create a "subject profile" in the system. In order to provide payment, the subject will need to enter their name and date of birth into their subject profile which is required to set up a subject account and for customer service purposes. Depending on which payment method is chosen, the subject may also need to enter their email address and banking information. If the subject already has an Advarra account (because they are in another study that uses this system), their existing profile will be used to provide payment.

Payments received for participation in research is considered taxable income. If the subject receives \$600.00 or more in any one calendar year from UR or its affiliates, the University is required to report this information to the Internal Revenue Service (IRS) in a 1099 (Miscellaneous Income) form. The subject will be sent a copy of this form and a copy will be sent to the IRS. Depending on the amount the subject is paid, they may be asked to submit a W-9 form, which includes their Social Security Number.

Potential benefits to the subjects

There are no benefits for the individual participant. The investigational medication may temporally improve or worsen the lesion in the target area of application. The nature of this pilot study does not promise benefit for the individual. We hope that this research will

